# 5.2.1.1 Storage Conditions

The study Investigator or designee is responsible for receiving each shipment of IP. Upon receipt of the IPs at the investigational site, the receipt procedures should be completed and IPs stored appropriately  $\leq$  -60°C. A record to account for all dispensing and return of unused IPs will be maintained by the investigational sites. At the end of the study the IPs will be reconciled. The Investigator will be fully responsible for the security, accessibility, and storage of the IPs while they are at the investigational facility.

Vials must be stored in the original vial storage boxes to facilitate supply tracking. It is recommended to leave the vial storage boxes in the original leak-proof bag or in a substitute leak-proof container, particularly if the supplies are not segregated (i.e., in a separate section of the freezer) from other products or biological samples.

The freezer should be in a locked or secured area, with limited access. Additionally, the freezer should have a temperature recorder and an alarm system. The temperature plot should be properly maintained and checked. Documentation for calibration of the freezer at installation and at each maintenance inspection should be available (at least annually or as per manufacturer's recommendations). A biohazard symbol should be affixed to the outside of the storage compartment.

# 5.2.1.2 Accountability and Compliance

The Investigator, pharmacist, or designee, may only dispense clinical supplies in accordance with this protocol.

The Investigator, pharmacist, or designee, is responsible for maintaining an accurate and current record of all clinical supplies received from Oncolys BioPharma Inc., dispensed to the Investigator or destroyed. Accountability records must be maintained throughout the course of the study, showing receipt and disposition of the clinical supplies.

At the end of the study, it must be possible to reconcile delivery records with that of used, unused and destroyed clinical supplies.

The Investigator is also responsible for the education of study staff in the correct administration of the IP.

Additional measures to ensure treatment compliance are not required because the IP will be prepared and administered by study personnel (see Section 5.2.1.3).

# 5.2.1.3 Study Material Preparation

OBP-301 should be prepared according to Biosafety Level 2 Guidelines, unless local regulations require a more rigorous containment level. An outline of Biosafety Level 2 precautions is located in the OBP-301 Pharmacy Brochure Appendix V: Handling Guidelines/Universal Precautions for Biosafety Level 2 Agents. Aseptic technique must be followed at all times during the preparation and transport of the IP to the treatment area. A disinfectant that has been qualified as an effective virucide for adenoviruses should be used for any decontamination procedure. The recommended exposure time should be at least 5 to 15 minutes. However, if the handling precautions recommended by the manufacturer differ, the manufacturer's instructions should be followed.

The duration that the IP remains at room temperature should be minimized and it is recommended that OBP-301 be administered as soon as possible (within 4 hours) after the OBP-301 is thawed. Immediately before injection, the IP may be warmed by rolling the syringe between the palms of the hands, which may facilitate comfort of administration to the patient.

The Investigator is responsible for the education of study staff in the correct administration of the IP and a designated staff member experienced in the administration of investigational agents directly into tumor lesions will administer all treatments.

# 5.2.1.4 Destruction of Used and Unused Investigational Product

Immediately after use, the used vials should be placed in a biohazardous waste container. Empty or partially used vials should be destroyed, by the study pharmacy, in accordance with institutional biosafety policy and procedures for biohazardous waste management. Proper accounting of the vials must be performed immediately using the Drug Accountability Form.

Written authorization must be obtained from Oncolys BioPharma Inc. before any destruction of unused clinical material supplies. This will occur at the completion of the clinical study or when the expiration date has been reached and could not be prolonged by Oncolys BioPharma Inc. based on updated stability information. In addition, destruction of unused supplies may only be performed after product reconciliation by the monitor.

The unused vials must be destroyed by the study pharmacy, in accordance with institutional Biosafety policy and procedures for biohazardous waste management or returned to Oncolys BioPharma Inc.

The Investigator or designee must fill in, sign, and date the appropriate section of Clinical Trial Material Destruction Certificate. Discrepancies in vial accountability must be explained in writing by the Investigator or designee. A copy will be retained for the site study file and the monitor will retrieve the original.

Further information of the storage, preparation, and administration of IP will be provided in the OBP-301 Pharmacy Brochure.

### 5.2.2 Selection and Timing and IP Administration for each Patient

OBP-301 ( $2 \times 10^{12}$  VP/vial) is administered as intratumoral injection into a primary gastric or GEJ tumor mass that is suitable for injection, eg greater than 1 cm in size and in a location amenable for endoscopic injection. For patients with tumors not assessible by endoscopy, injection via interventional radiology procedure is permitted, applying the same dosing principles described herein. The largest diameter of the lesion will determine the volume of OBP-301 injected. The rationale for this is to ensure adequate penetration of the viral particals throughout the tumor.

### Safety Guidelines for Clinical Study Patients and Caregivers

- Avoid direct contact with body fluids of patients who were injected with OBP-301.
- Immunocompromised individuals or pregnant women should not come into direct contact with body fluids of treated patients.

### Safety Guidelines for Healthcare Staff when Handling OBP-301

- Immunocompromised individuals or pregnant women should not prepare or administer OBP-301 and should not come into direct contact with OBP-301 injection sites, dressings, or body fluids of treated patients.
- Staff must follow Biosafety Level 2 guidelines by avoiding accidental exposure to OBP-301 and follow the instructions for preparation, administration, and handling of OBP-301.
- Staff must wear personal protective equipment (protective gown or laboratory coat, safety glasses or face shield, and gloves) while preparing or administering OBP-301.
- Cover any exposed wounds before handling OBP-301.
- In the event of an accidental occupational exposure (e.g., through a splash to the eyes or mucous membranes), flush with clean water for at least 15 minutes.
- In the event of exposure to broken skin or needle stick, clean the affected area thoroughly with soap and water and/or a disinfectant.
- Clean all surfaces that may have come in contact with OBP-301 and treat all spills with a virucidal agent such as 1% sodium hypochlorite or 70% isopropyl alcohol and blot using absorbent materials.
- Dispose of all materials that may have come in contact with OBP-301 (e.g., vial, syringe, needle, cotton gauze, gloves, masks, or dressings) as biohazardous waste.

# 5.2.3 Injection Procedures

The optimum technique for injection of a primary tumor is to inject the viral particles circumferentailly around the lesion in 4 quadrants, similar to the technique used in endoscopic submucosal disection (Gotoda T, et al. J Gastroenterol 2006;41:929-942.). This will ensure that the viral partical will be maximally penetrated into the lesion.

Endoscopists who perform single polypectomies will be eligible to perform the procedure. A trianing video (prepared by Oncolys Biopharma) is available as well.

The procedure will be performed in the Endoscopy Unit or interventional suite with standard sterilization procedures. A standard gastroscope and needle (eg. GIF-HQ190 Olympus gastroscope with 25 gauge Carr-Locke injection needel made by US Endoscopy) is used for the procedure. Guidelines for each injection procedure are provided below.
#### Pre-Injection

- Confirmation of eligiblity
- Review of medications
- Abbreviated physical exam and performance status
- Vital signs

# Post-Injection

- Monitor patient for 60-90 minutes for any symptoms of injection site pain, bleeding, nausea.
- Vital signs (except weight)

Standard sedation procedures used for endoscopy will be used, and consists of monitored anesthesia care with an anesthesiologist and the patient monitored at all times. OBP-301 may be associated with injection site pain if administered to dermal lesions. However, pain has not been observed for intralumenal injections previously.

# 5.2.4 Dose Delay and Adjustment

# Pembrolizumab

Pembrolizumab is given at a flat dose of 200 mg IV every 3 weeks, per institutional guidelines. There are no dose modifications to this treatment.

Adverse events (both non-serious and serious) associated with pembrolizumab exposure may represent an immunologic etiology. These adverse events may occur shortly after the first dose or several months after the last dose of treatment. Pembrolizumab must be withheld for drug-related toxicities and severe or life-threatening AEs as per Table 2 below. See Section 5.2.2.6 and Events of Clinical Interest Guidance Document for supportive care guidelines, including use of corticosteroids.

**Table 2**. Dose Modification Guidelines for Pembrolizumab -Related Adverse Events (as per package insert).

Toxicit y	Hold Treatme nt For Grade	Timing for Restarting Treatment	Discontinue Subject from Study Treatment
Diarrhe a/Coliti s	2-3	Toxicity resolves to Grade 0- 1.	Toxicity does not resolve within 12 weeks of last dose or inability to reduce corticosteroid to 10 mg or less of prednisone or equivalent per day within 12 weeks.

Toxicit y	Hold Treatme nt For Grade	Timing for Restarting Treatment	Discontinue Subject from Study Treatment
	4	Permanently discontinue	Permanently discontinue
AST, ALT,	2	Toxicity resolves to Grade 0-1	Toxicity does not resolve within 12 weeks of last dose.
or Increas ed Bilirubi n	3-4 Permanently discontinue		Permanently discontinue
Type 1 diabete s mellitus (if new onset) or Hyperg lycemia	T1DM or 3-4	Hold pembrolizumab for new onset Type 1 diabetes mellitus or Grade 3-4 hyperglycemia associated with evidence of beta cell failure.	Resume pembrolizumab when patients are clinically and metabolically stable.
Hypoph ysitis	2-3	Toxicity resolves to Grade 0-1	Toxicity does not resolve within 12 weeks of last dose or inability to reduce corticosteroid to 10 mg or less of prednisone or equivalent per day within 12 weeks.
	4	Permanently discontinue	Permanently discontinue
Hypert hyroidi sm	3	Toxicity resolves to Grade 0-1	Toxicity does not resolve within 12 weeks of last dose or inability to reduce corticosteroid to 10 mg or less of prednisone or equivalent per day within 12 weeks.
	4	Permanently discontinue	Permanently discontinue
Hypoth yroidis m	2-4	Therapy with pembrolizumab can be continued while treatment for the thyroid disorder is instituted	Therapy with pembrolizumab can be continued while treatment for the thyroid disorder is instituted.
Infusio n	3-4	Permanently discontinue	Permanently discontinue

Page 40 V8.0

Toxicit y	Hold Treatme nt For Grade	Timing for Restarting Treatment	Discontinue Subject from Study Treatment
Reactio n			
Pneum onitis	2	Toxicity resolves to Grade 0-1	Toxicity does not resolve within 12 weeks of last dose or inability to reduce corticosteroid to 10 mg or less of prednisone or equivalent per day within 12 weeks.
	3-4	Permanently discontinue	Permanently discontinue
Renal Failure or Nephrit is	2	Toxicity resolves to Grade 0-1	Toxicity does not resolve within 12 weeks of last dose or inability to reduce corticosteroid to 10 mg or less of prednisone or equivalent per day within 12 weeks.
15	3-4	Permanently discontinue	Permanently discontinue
All Other Drug- Related Toxicit	3 or Severe	Toxicity resolves to Grade 0-1	Toxicity does not resolve within 12 weeks of last dose or inability to reduce corticosteroid to 10 mg or less of prednisone or equivalent per day within 12 weeks.
y 	4	Permanently discontinue	Permanently discontinue

Note: Permanently discontinue for any severe or Grade 3 drug-related AE that recurs or any life-threatening event.

 For patients with liver metastasis who begin treatment with Grade 2 AST or ALT, if AST or ALT increases by greater than or equal to 50% relative to baseline and lasts for at least 1 week then patients should be discontinued.

 Patients with intolerable or persistent Grade 2 drug-related AE may hold study medication at physician discretion. Permanently discontinue study drug for persistent Grade 2 adverse reactions for which treatment with study drug has been held, that do not recover to Grade 0-1 within 12 weeks of the last dose.

# OBP-301

OBP-301 injection will be delayed for any ongoing Grade 3 toxicity attributable to OBP-301 at the time of the next scheduled injection. Patients who require a delay of OBP-301 injection of > 4 weeks (i.e., approximately 6 weeks from the previous injection) due to lack of resolution to

Grade 1 toxicity will be discontinued from the study. In this circumstance, the patient will be evaluable for toxicity, but will be replaced (up to the maximum enrollment) for efficacy assessment.

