# 6.1.4 Patient Withdrawal Criteria

In accordance with applicable regulations, a participant has the right to withdraw from the study, at any time and for any reason, without prejudice to his future medical care.

Withdrawal from the study and therapeutic measures taken shall be at the discretion of the Investigator. A full explanation for the discontinuation from the study should be made in the participant's medical records and in the eCRF.

Premature discontinuation from active study participation may occur at any time due to any of the following reasons:

- Any situation where, in the opinion of the Investigator or the Medical Monitor, continued participation in the study would not be in the best interest of the patient.
- Positive pregnancy test
- Patient initiates other anti-cancer therapy. The anti-cancer therapy will be documented in the medical record and eCRF.
- Progressive neoplastic disease, unless the Investigator feels this may be pseudoprogression, in which case the patient may remain on study until the next evaluation for extent of disease.
- An intercurrent illness or AE that requires concomitant medication that precludes further study participation
- Patient is unable or unwilling to comply with study procedures.
- Patient is lost to follow-up.
- Patient withdraws consent.
- Termination of the study by the Sponsor.
- Request by a Health Authority.

In addition, the Sponsor will discontinue a patient from active study treatment for any of the following criteria (subjects will continue to be followed as apprioprate for outcomes and toxicities:

- Patients who experience a Grade 4 hematologic toxicity or a Grade 3 or greater nonhematologic toxicity attributable to OBP-301 or the endoscopic procedure that has not resolved to Grade 1 (or basline) within 2 weeks of onset.
- OBP-301 injection will be delayed for any ongoing Grade 2 toxicity at the time of the next scheduled injection after consultation with the Principal Investigator. Patients who require a delay of OBP-301 injection of > 4 weeks (i.e., approximately 6 weeks from the previous injection) due to lack of resolution to Grade 1 toxicity will be discontinued from the study after consultation with Medical Monitor and Principal Investigator.

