After apparent disease progression (PD) is observed, administration of OBP-301 may be continued as per iRECIST. Immune-related disease progression (irPD) will be confirmed if the increase in tumor burden is  $\geq 25\%$  relative to nadir (minimum recorded tumor burden). The confirmation is completed by a repeat, consecutive assessment no less than 4 weeks from the date the disease progression was first documented. If in the opinion of the investigator, the disease progression is not clinically significant, then the patient may continue to receive OBP-301 treatment.

The reason(s) for premature study discontinuation/withdrawal will be documented along with the date of withdrawal. AEs should be documented according to the study calendar.

For all patients who discontinue, a Final Visit will be performed within  $28 \pm 5$  days after the last IP administration (see study calendar). If a participant is withdrawn because of an AE, the Investigator must arrange for the participant to have appropriate follow-up care until the AE is

resolved or has stabilized. Unresolved AEs will be followed until the last scheduled follow-up visit or until the Investigator and Medical Monitor determine that further follow-up is no longer indicated. Investigators should attempt to collect the survival information as dictated by the Schedule of Events in the Study calendar.

Patients who discontinue the active study participation will not be replaced.

Any enrolled patients who are discontinued before study dosing will be documented as screen failures in the eCRF and replaced. No follow-up is required for these patients.

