# 8.4.2 Evaluable Population

Any patient that has at least one radiographic assessment for response will be included in the Efficacy Population. Imaging studies preferably CT scan of the chest/abdomen/pelvis will be performed every 9 weeks as per the study schedule. Patients will be evaluated according to RECIST v1.1 criteria. Definitions of response evaluation are detailed in section 6.6 for further explanation. Only those patients whose response can be measured according to RECIST v1.1 will be included in this population.

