# 8.4.3 Intent-to-Treat (ITT) Population

All patients who are enrolled and allocated to treatment are included in the intent-to-treat population analysis.

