# 8.5.4 Methods for Analysis

Endpoints involving response rates will be analysed by tabulating the response rates along with 95% confidence interval and number of patients with data for each time point that the endpoint is collected. Waterfall plots for tumor response (CR, PR, and ORR) will be provided.

Endpoints involving time to event or time to response will be analysed using survival analysis, including Kaplan-Meier plots. Median survival time with 95% confidence interval, 25th-75th percentiles will be provided.

Exploratory subgroup analyses for tumor response will be defined in the statistical analysis plan (SAP).

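### The protocol both replaces and does not replace a dosed patient discontinued after an OBP-301 delay of more than 4 weeks, and section 8 would still count that patient if scanned

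*Combined protocol and SAP*

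**What the plan says.** Section 5.2.4 (OBP-301) delays an injection for ongoing Grade 3 toxicity attributable to OBP-301. If the delay exceeds 4 weeks because toxicity has not resolved to Grade 1, the patient is discontinued, and then "the patient will be evaluable for toxicity, but will be replaced (up to the maximum enrollment) for efficacy assessment".

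Section 6.1.4 covers the same discontinuation: "Patients who require a delay of OBP-301 injection of > 4 weeks" for lack of resolution to Grade 1 leave the study, here after consultation with the Medical Monitor and Principal Investigator. Its delay is triggered by any ongoing Grade 2 toxicity, also after consultation. The section closes with "Patients who discontinue the active study participation will not be replaced" and allows replacement only for patients discontinued before dosing. Section 4.5.1 repeats both of those closing sentences but does not list the delay among its reasons.

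A separate item in 6.1.4 stops active treatment for "Grade 3 or greater nonhematologic toxicity attributable to OBP-301 or the endoscopic procedure that has not resolved to Grade 1" within 2 weeks of onset. Of the patients stopped under its added criteria, 6.1.4 says "subjects will continue to be followed as apprioprate for outcomes and toxicities".

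Section 8 does not mention replacement. Section 8.4.2 says "Any patient that has at least one radiographic assessment for response will be included in the Efficacy Population", and its last sentence limits the population to patients whose response can be measured. Section 8.8 applies the stage 1 rule to the first 18 evaluable patients and the final rule to 37 patients entered; the synopsis and 3.1 describe the 37 as evaluable. Section 8.4.3 adds that "All patients who are enrolled and allocated to treatment are included in the intent-to-treat population analysis". Section 8.5.4 says "Endpoints involving response rates will be analysed by tabulating the response rates along with 95% confidence interval and number of patients with data". Neither 8.5.1 nor 8.5.4 names the population for the primary response rate.

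**The concern.** A site with a dosed patient whose injection has been held for more than 4 weeks finds two instructions: enrol a replacement, or do not. No section cross-refers to another. The difference in delay trigger (attributable Grade 3 against any Grade 2) means that the number of patients affected also depends on which section is followed.

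The primary decision is a small count: at least 3 responders in 18 to continue and at least 9 in 37 to succeed. Replacement takes a treated patient out of that count because of study-drug toxicity; no replacement keeps the place. If the patient is replaced under 5.2.4 but has a scan, 8.4.2 still admits that patient, so patient and replacement could both be counted. Deferring details to a SAP, as 8.1 does, cannot settle this, because replacement is decided during enrolment from the protocol text.

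**Working it through.** **Inputs.** From 8.8: null rate 15%, target rate 30%, 10% significance level, 80% power, stop at 2 or fewer of 18, success at 9 or more of 37, and 41 enrolled, which leaves 41 - 37 = 4 spare places. From 1.1.2: no dose-limiting toxicity in 22 phase I patients. The share of patients discontinued for a long delay is not given, so 0 to 4 removals, or 2-10% per patient, is an assumed range.

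**1. The plan's own figure.** P(success) = sum over x = 3 to 18 of Bin(x; 18, p) × P(Y ≥ 9 - x), with Y ~ Bin(19, p). This gives 0.0875 at p = 0.15 and 0.8060 at p = 0.30. The stated properties hold.

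**2. Replacement, worst case.** Assume that removed patients never respond and that 15% is the rate in all treated patients. With k removals in stage 1, 18 + k patients are treated to obtain 18 counted, so the rate among those counted is 0.15 × (18 + k)/18. With all k in stage 2 it is 0.15 × (19 + k)/19.

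| Removals | Counted rate, all in stage 2 | False-positive rate | Counted rate, all in stage 1 | False-positive rate |
|---|---|---|---|---|
| 1 | 0.1579 | 0.0987 | 0.1583 | 0.1005 |
| 2 | 0.1658 | 0.1106 | 0.1667 | 0.1146 |
| 4 | 0.1816 | 0.1360 | 0.1833 | 0.1456 |

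One removal spread evenly over the 37, rate 0.15 × 38/37, gives 0.0997. If removal is unrelated to response, or if 15% is the rate among evaluable patients, the figure stays at 0.0875 with the count held at 18 and 37.

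**3. Patient and replacement both counted.** If one extra patient were counted on unchanged cut-offs, with everyone responding at 15%, the false-positive rate would be 0.0990 (extra patient in stage 2) to 0.1011 (in stage 1). This needs the count to run past 18 or 37, for which 8.8 has no cut-off.

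**4. No replacement.** Keep k non-responders in the 37 and let the others respond at 30%, so that Bin(18 - k) or Bin(19 - k) replaces the full stage. Power is 0.7736 (stage 1) to 0.7817 (stage 2) for k = 1, and 0.7370 to 0.7542 for k = 2.

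**5. A stage 1 decision that turns on the rule.** Take one removed non-responder among the first 18, 2 responders among the other 17, and a replacement who responds. The trial continues with replacement (3 of 18) and stops without it (2 of 18). Given exactly one removal, the probability is Bin(2; 17, p) × p: 0.2673 × 0.15 = 0.0401 at 15%, and 0.0581 × 0.30 = 0.0174 at 30%. The chance of exactly one removal among 18 is 18d(1 - d)^17 = 0.255, 0.376 and 0.300 at d = 2%, 5% and 10%. The joint probabilities are 0.0102, 0.0151 and 0.0120 at 15%, and 0.0045, 0.0066 and 0.0052 at 30%: that is, 1.0-1.5% and 0.4-0.7%.

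**6. How many removals to expect.** The one-sided 95% upper limit for 0 of 22 is 1 - 0.05^(1/22) = 12.7%. Dose-limiting toxicity is only a proxy for a long delay, and dose and schedule differed.

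**The case against.** 5.2.4 can be read as a specific exception to a general rule. That would answer 4.5.1, which does not list the delay. It does not answer 6.1.4, which names this discontinuation and still ends with no replacement.

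A reader might infer that section 8 leaves the count undefined. It does not. Section 8.4.2 with the stage 1 rule in 8.8 supplies a default: a patient with a response scan is counted. The schedule of events places imaging at End of Study, 28 days after removal, so many removed patients should have a scan. The synopsis and 3.1 also settle that the 37 are evaluable patients. What remains is that this default contradicts 5.2.4.

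A reader might also infer that the 10% error level is breached. The documents do not support that as a general statement. It needs both assumptions in step 2, and the design is framed in evaluable patients. Even under those assumptions one removal gives about 10%. Few removals are likely: beyond the 22 phase I patients, 1.1.2 reports no dose-limiting events in 13 esophageal patients given OBP-301 with radiation, and none in 3 subjects given a single dose of 3×10^12 VP. If 6.1.4 is followed, its 2-week item would stop some patients before a 4-week delay accrues. Whether patients stopped under that item fall under the no-replacement sentence is itself an inference, since the item concerns study treatment and the sentence concerns study participation.

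Nothing in the documents suggests that anyone would choose between the rules after seeing responses, and a DSMB reviews interim data. The text merely does not rule it out.

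Finally, writing the exception into 4.5.1 and 6.1.4 would also remove the contradiction and would avoid the power loss in step 4. That is a legitimate alternative, but it keeps toxicity-based removal from the primary count and would still require 8.4.2 to change.

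**Conclusion.** The contradiction stands: the plan cannot be followed as written for a dosed patient discontinued after a delay of more than 4 weeks, and the choice of rule bears on the counts that decide the trial. It should be corrected, ideally before the stage 1 decision.

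The numerical effect is probably small. The 13.6-14.6% for four removals is an upper bound: it uses every spare place, which replacements share with all other unevaluable or ineligible patients, and rests on both worst-case assumptions. The stage 1 pattern in step 5 is rare under either response rate. All these sizes depend on a removal rate that the documents do not give.

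**What to change.** Delete the replacement sentence in 5.2.4 so that it agrees with 4.5.1 and 6.1.4, and use one delay trigger in 5.2.4 and 6.1.4. State in 5.2.4, 6.1.4, 8.4.2 and 8.8 that a patient who has received at least one OBP-301 injection and is discontinued for toxicity is not replaced, keeps their place in the 18 or the 37, and counts as a non-responder unless a response is documented. Amend the last sentence of 8.4.2, which would otherwise exclude such a patient without a measurable response, and reword the 37 entered in 8.8 to mean the 37 counted under 8.4.2. Report the response rate in all treated patients (the Safety Population of 8.4.1) beside the primary result.

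The cost is wording in four sections and one response table, with no extra patients. The statistical cost is the loss shown in step 4: if 30% is the rate among patients who are not removed, power drops below the planned 80%, to 73.7-75.4% with two retained non-responders. The four spare places remain for ineligible or otherwise unevaluable patients. Replacing patients who progress or die before a scan is a separate source of selection that this change does not remove; the all-treated response rate would make it visible.
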